7.5.4 Rescue Medications

The number of rescue medication days during the treatment period will be compared to the number of rescue medication days during the 2-week washout period (Day -14 to -1) using:

- 4-week treatment period:
 - Day 1 to Day of Visit 4 1 for all 4 weeks of treatment (Weeks 1 4)
- 2-week intervals of the treatment period:
 - Day 1 to Day of Visit 3-1 for first 2 weeks of treatment (Weeks 1-2)
 - Day of Visit 3 to Day of Visit 4 1 for last 2 weeks of treatment (Weeks 3 4)
- 4-week follow-up period:
 - Day of Visit 4 to Day of Visit 5 1 for all 4 weeks of follow-up (Weeks 5 8)
 - 2-week intervals of the follow-up period:
 - Day of Visit 4 to Day of Visit 4 + 13 for first 2 weeks of follow-up (Weeks 5 6)

Protocol: PRB244-01 STATISTICAL ANALYSIS PLAN Confidential

Version 3.0 12-Jan-22

Day of Visit 4 + 14 to Day of Visit 5 - 1 for last 2 weeks of follow-up (Weeks 7 - 8)

Each time interval will be normalized as a rate using the following formula:

$$\# rescue medication \ days = \left(\frac{\# \ days \ rescue \ medications \ used \ in \ interval}{\# \ actual \ days \ in \ interval}\right) * \# \ expected \ days \ in \ interval$$

For example, if there are 30 days in the Week 4 interval (the 2 weeks between visits 3 and 4), and a subject uses rescue medications for 7 of those 30 days, then the formula will be calculated as (7/30)*14=3.27. That is, 3.27 rescue medication days should be reported for the interval covering Weeks 3 and 4.

Change in rescue medication days from Baseline to each post-baseline visit will be tabulated. Number of rescue medication days per 2-week interval and per study period (treatment, followup) will be listed.

The use of any of the allowed rescue medications in the rescue medication diary data will be counted for the rescue medication days. If multiple rescue medications are reported on a single date, that date is still counted as only 1 rescue medication day. "Other" rescue medication selected in the daily diary will be confirmed to be one of the allowed rescue medications, and only the allowed rescue medications will be included as rescue medication days while others will not (such as other concomitant medications or prohibited medications).

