6.5.6 Rescue Medication During Treatment Period

The treatment period (also referenced as "on-treatment") begins on date of subject's first dose and ends on Day of Visit 4 - 1, even if the subject has applied IP on Day of Visit 4.

Based on recorded use of rescue medication the following variables will be derived and normalized as described in section 7.5.4 for all subjects:

- Number of days in a month with rescue treatment (for Week 1 to Week 4 and Week 5 to Week 8)
- Number of days every 2 weeks with rescue treatment (for Day -14 to -1 for Baseline, Day 1 to Day of Visit 3 -1 for Week 2, Day of Visit 3 to Day of Visit 4 -1 for Week 4, Day of Visit 4 to Day of Visit 4 + 13 for Week 6, and Day of Visit 4 + 14 to Day of Visit 5 1 for Week 8)

Proportion of subjects with rescue treatment, and the above two variables (number of days in a month with rescue treatment and number of days every 2 weeks with rescue treatment) will be derived and normalized for subjects with recorded use of rescue medication.

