7.4 Efficacy Analysis

All efficacy analyses will be performed on the mITT population and PP population using the methods described below. Regression models will include all eligible subjects for the respective analysis, from the 3 treatment arms.

- *Primary Analysis*: Includes data for all subjects in the respective population (mITT/PP)
- *Sub-Analysis*: Excludes data collected on/after date of first on-treatment rescue medication use through the end of the study.
 - For WI-NRS/AI-NRS endpoints, excludes data from *week* of first on-treatment rescue medication use.
- *Non-Responder Imputation (NRI) Analysis*: Subjects who discontinue treatment early or who take on-treatment rescue medications will be imputed as a non-responder for assessments that occur on/after date of discontinuation/on-treatment rescue medication use through the end of the study.

STATISTICAL ANALYSIS PLAN

Version 3.0 12-Jan-22

- For WI-NRS/AI-NRS endpoints, excludes data from *week* of discontinuation/first on-treatment rescue medication use.
- Subjects who discontinue early should have at least one treatment-emergent adverse event (TEAE) leading to discontinuation in order to have their data imputed for NRI analysis.

| Efficacy Analyses | lyses | A | cacy | Effi |
|-------------------|-------|---|------|------|
|-------------------|-------|---|------|------|

| Measure | Endpoints | Analysis |
|--------------------|---|--|
| WI-NRS/ AI-NRS* | Mean Change from Baseline | Primary Primary/Sensitivity Sub-Analysis Sub-Analysis/Sensitivity |
| WI-NRS/ | Improvement | Primary Primary/Sensitivity Sub-Analysis Sub-Analysis/Sensitivity NRI NRI |
| AI-NKS* | (4-Point, Any) | 6. NRI/Sensitivity |
| 5D | Mean Change from Baseline | 2. Sub-Analysis |
| EASI | Mean Change from Baseline | Primary Sub-Analysis |
| EASI | Improvement (≥50%, ≥75%, ≥90%) | 1. Primary 2. Sub-Analysis 3. NRI |
| IGA | Mean Change from Baseline | 1. Primary 2. Sub-Analysis |
| IGA | Improvement (2-Point to Clear/Almost Clear, Clear/Almost Clear, Any) | Primary Sub-Analysis NRI |
| POEM | Mean Change from Baseline | Primary Sub-Analysis |

*WI-NRS/AI-NRS analyses require at least 1 diary entry per week to calculate the weekly average, except for the sensitivity analyses, where at least 4 diary entries per week are required.

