PP population excludes subjects with any major protocol deviation that may impact efficacy and safety analyses, including those with any confounding events or those over the rescue medication use limits but includes data for subjects below rescue medication use limits. Rescue medication

STATISTICAL ANALYSIS PLAN

Version 3.0 12-Jan-22

use below the allowed limit per protocol are considered minor protocol deviations, are considered non-confounding, and is included in the PP population.

The following events are confounding:

- Change in stable use of oral H1 antihistamines (e.g., change in type, dose, and frequency of medication)
- Change in stable use of bland emollients (e.g., change in type, dose, and frequency of treatment)
- Use of excluded medications during study
- Use of rescue medications over the allowed limit per protocol (over 3 rescue medication days during the 2-week washout period, over 7 rescue medication days during the 4-week treatment, and over 7 rescue medication days during the 4-week follow-up)

In the PP sub-analysis, all subject data over the rescue medication limits per the PP primary analysis will be excluded, but subject data below the rescue medication limits will be included up to the date or week that the first rescue medication is taken.

Hypothesis tests for the primary efficacy endpoint will be performed using a Dunnett Testing Method, applying pairwise comparisons of each respective B244 dose group to vehicle using a one-sided familywise error rate of 0.10. Section 7.4.2 provides further details. No additional adjustments will be made for multiple testing. As such, p-values from analysis of secondary and exploratory efficacy analyses must be interpreted in an exploratory fashion.

Supportive analyses may be performed for all efficacy analyses combining the B244 dose groups in comparison against vehicle and comparison of the B244 groups to one another.

Furthermore, stratified analyses will be performed by presenting descriptive statistics by age group, race, gender, IGA at Baseline (2 or 3), EASI at baseline (≤ 10 or >10), BSA range at Baseline (10 to 20%, >20 to 30%, >30 to 40%), rescue treatment used at Baseline (Yes, No), and rescue medication used while on treatment (Yes/No).

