A Phase II, Randomized, Double-Blind, Vehicle Controlled Study of the Efficacy, Safety, and Tolerability of B244 Topical Spray for the Treatment of Pruritus in Adults with a History of Atopic Dermatitis

Sponsor:

AOBiome, LLC [name]

ADDENDUM TO SAP v3.0

Version 1.0 22-Apr-22

ADDENDUM TO SAP REVIEW AND APPROVAL

This Addendum to Statistical Analysis Plan v3.0 (12Jan2022) has been prepared in accordance with team reviewers' specifications.

| Prepared by: [name]. Signing Reason: 1 am the author of this document Signing Time: 03 May 2022 4:44:40 AM PDT F18BA 1C2EF7C48A4B775BE54652AC840 | 03 May 2022 |
|--|------------------|
| [name], Bio-Statistician | Date |
| Sponsor Review: | 05 May 2022 |
| [name], Bio-Statistician | Date 05 May 2022 |
| [name], VP of Clinical Operations | Date |

ADDENDUM TO SAP v3.0

Version 1.0 22-Apr-22

Table of Contents

| 1 | Background and Purpose | . 4 |
|---|--|-----|
| 2 | Request 1: Worst Case Analysis | . 4 |
| 3 | Request 2: Intention-to-Treat Analysis | . 5 |
| 4 | List of Tables | . 6 |
| 5 | Table Shells | . 8 |

ADDENDUM TO SAP v3.0

Version 1.0 22-Apr-22

1 Background and Purpose

The purpose of this addendum to the final Statistical Analysis Plan (SAP) for the PRB244-01 study (v3.0 dated 12Jan2022) is to describe additional statistical analyses that will be performed in order to address requests by the FDA made on 27Mar2022. These requests are detailed in the sections below.

2 Request 1: Worst Case Analysis

FDA Request: You proposed the non-responder imputation analysis in which subjects who discontinue treatment early or who take on-treatment rescue medications will be imputed as a non-responder. Similar to the non-responder imputation analysis, we recommend that you provide additional analyses on the primary efficacy endpoint and relevant efficacy endpoints in which the underlying score-based variable values (e.g., WI-NRS, AI-NRS, IGA, etc.), are imputed with the worst score on/after date of first rescue medication use through the end of the study.

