As a parallel to the non-responder imputation analysis, for score-based endpoints of WI-NRS, AI-NRS, IGA, and EASI, we will perform worst-value imputation on/after the date of first ontreatment rescue medication or date of subject early discontinuation through the end of the study. For this sensitivity analysis, all values on/after the date of first on-treatment rescue medication use or all values missing due to subject early discontinuation will be replaced with the worst value observed for each subject between first post-baseline assessment and first use of ontreatment rescue medication (WOCF). In the event there is no observation after baseline recorded, WOCF will be Baseline values.

Subjects who discontinue early should have (1) at least one treatment-emergent adverse event (TEAE) leading to discontinuation and (2) discontinuation occurring prior to their Week 4 visit in order to have their data imputed for WOCF analysis.

In cases where subjects completed the treatment period, but did not complete all of the follow-up period, the following logic will be used in order to fully parallel the NRI analysis. If subjects use rescue medications while on treatment and discontinue after the Week 4 visit, then only values from first on-treatment rescue medication use through last attended visit will be imputed with WOCF (i.e., missing data from visits that did not occur after Week 4 would not be imputed in this case).

The mITT population will be used for this analysis. For WOCF imputation of WI-NRS and AI-NRS values, the worst-observation would be the highest weekly average (not highest daily score) reported after baseline and before first on-treatment rescue medication use or before subject early discontinuation.

ADDENDUM TO SAP v3.0

Version 1.0 22-Apr-22

If a situation occurs where a visit is missed but a subsequent visit takes place for the same subject, then the missing data for that interim visit will not be imputed unless that visit occurs on/after the date of first on-treatment medication use.

3 Request 2: Intention-to-Treat Analysis

FDA Request: We recommend that you perform additional sensitivity analyses to include dropouts for whom no single score is collected and thus missing data handling strategies are to be considered. In this analysis, the analysis population will be the intent-to-treat (ITT) population.

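### Excluded therapy taken for eczema or itch appears not to trigger the mITT Sub-Analysis, NRI or WOCF, because the trigger is undefined and the only rule on rescue leaves it out

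*SAP*

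**What the plan says.** SAP 7.4 defines the Sub-Analysis by this rule: "Excludes data collected on/after date of first on-treatment rescue medication use through the end of the study". For WI-NRS and AI-NRS the cut falls at the week of first use. NRI treats a subject as a non-responder from on-treatment rescue or from early discontinuation, with a condition on the latter: "Subjects who discontinue early should have at least one treatment-emergent adverse event (TEAE) leading to discontinuation in order to have their data imputed".

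Section 2 of the addendum sets the WOCF, under which "all values on/after the date of first on-treatment rescue medication use or all values missing due to subject early discontinuation will be replaced" by the subject's worst post-baseline value before that use. It too requires a TEAE leading to discontinuation, and the discontinuation must precede the Week 4 visit. On population it says: "The mITT population will be used for this analysis". The regulator's request, as reproduced there, asks that scores "are imputed with the worst score on/after date of first rescue medication use through the end of the study".

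What counts as rescue is settled only in SAP 7.5.4, for day counts: "only the allowed rescue medications will be included as rescue medication days while others will not (such as other concomitant medications or prohibited medications". SAP 6.5.6, which fixes the treatment period, sends its rescue variables to that section: "Based on recorded use of rescue medication the following variables will be derived and normalized as described in section 7.5.4 for all subjects". Footnotes to Table 14.3.8.3 and Listing 16.2.13.2 apply the same allowed-list filter to diary entries marked Other.

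Excluded medication appears in SAP 7.4 as a separate confounding event, "Use of excluded medications during study", which removes a subject from the PP population. Protocol 8.9 and 8.14.2 take a subject who uses excluded therapy for eczema or itch off study drug.

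**The concern.** These three analyses serve to stop other eczema treatment from passing as benefit of study drug. Protocol Appendix B bars Class 1-3 topical steroids as high-potency and allows Class 4-7. If the trigger follows 7.5.4, one day of a permitted Class 7 hydrocortisone starts censoring, non-response and worst-value imputation. A barred Class 1 steroid or a systemic steroid used for the same itch starts none of them by itself. A low Week 4 itch score obtained with the barred product could then stand in analyses meant to screen it out. This ordering is documented for topical steroids; it is not claimed for every item in Appendix B.

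**Working it through.** No stated figure in the plan is at issue, so the main check sets the rules side by side. Entries show what each rule does in the mITT population.

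| Analysis | Permitted rescue | Excluded therapy for eczema or itch | Study drug stopped, no TEAE | Study drug stopped for a TEAE |
|---|---|---|---|---|
| Sub-Analysis (7.4) | data dropped | no rule | no rule | no rule |
| NRI, text of 7.4 | non-responder | no rule | not imputed | non-responder |
| NRI, shell footnotes (e.g. Tables 14.2.2.5.5 and 14.2.2.13.3) | non-responder | no rule | non-responder | non-responder |
| WOCF (Addendum 2) | worst value | no rule | not imputed | worst value, if before the Week 4 visit |

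**Can the affected subject have Week 4 data?** Yes. Protocol 8.9 keeps an early termination visit and a follow-up visit after study drug is stopped. Appendix A schedules daily WI-NRS through follow-up. SAP 6.5.3 forms a weekly mean from a single diary entry.

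**Who falls in the gap?** A mITT subject who meets all four conditions:

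1. on-treatment use of excluded therapy for eczema or itch;
2. no earlier on-treatment permitted rescue, which would already trigger all three analyses through study end;
3. no TEAE leading to discontinuation;
4. Week 4 data present. Without them the subject is missing rather than a responder, because the denominator in Table 14.2.2.5.1 is subjects with data at the visit.

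A TEAE does not bring the subject into the Sub-Analysis, which has no discontinuation rule.

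**Leverage per subject.** N = 160 evaluable per arm (SAP 7.1). Relabelling a subject who has data leaves N unchanged.

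- NRI rate: 1/160 = 0.00625, or 0.6 percentage points if the subject is counted as a responder, and 0 if not. With the 192 planned for randomization per arm, 1/192 = 0.5 points.
- WOCF mean: d/160 per subject, where d is the WOCF value minus the kept Week 4 WI-NRS. Each point of d moves the arm mean by 1/160 = 0.006. The WOCF value is the worst weekly average before the trigger, or baseline if there is none. A subject who is still flaring at Week 4 can equal or exceed it, so d can be positive, zero or negative, and no signed range is justified.
- Difference between arms: for NRI, (responders affected in one arm minus those in the other)/160, which is 0 if the arms are alike.
- Primary ANCOVA: 0, since footnote 3 of Table 14.2.2.1 excludes no data for rescue.

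**The case against.** **The trigger is undefined, not narrowed.** The 7.5.4 sentence governs a count of days, the table and listing footnotes govern displays, and 6.5.6 links only day-count variables to 7.5.4. Protocol 8.14.1 also opens in broad terms before it lists permitted products. This stands in part: a reader might infer that the SAP expressly excludes barred therapy from the trigger, and it does not. The narrower reading is an inference. It is the better-supported one, though, because SAP 7.4 lists excluded medication apart from over-limit rescue, Protocol 8.14.2 treats excluded therapy as lying outside the rescue allowance, and nothing in either document points to a wider trigger.

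**The NRI shells may close the gap.** Their footnotes impute every early treatment discontinuation with no TEAE condition, and the protocol requires such subjects to stop study drug. This stands for NRI on that wording. The text of 7.4 says otherwise, and the Sub-Analysis, the WOCF and subjects not actually taken off drug remain open.

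**The group is narrow.** Four conditions must coincide, and under Protocol 13.1 an exacerbation is itself an AE, so a flare that ends treatment may well carry a qualifying TEAE. This stands, and it limits the size of the point.

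**PP already deals with it, and the regulator named only rescue.** PP does remove these subjects. It also removes those with other major deviations, no Week 4 visit or under 50% of product used, so it does not repair the mITT results. The regulator's wording is a reason to keep the WOCF as planned, and the fix does so.

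**Conclusion.** The point holds as a gap in three supportive mITT analyses and merits a low-cost improvement. It rests on one inference, that the allowed-list rule in 7.5.4 carries over to the trigger. If the sponsor intended a wider trigger, a sentence saying so is still needed.

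The documents give no rate of excluded-therapy use, so neither the size of the group nor the direction of any bias can be derived. The figure of 0.6 percentage points on an arm's NRI rate is for one affected responder among 160. Bias between arms arises only if such use, or response after it, differs by arm.

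A reader might infer that these analyses favour B244, or that the primary result is compromised. The documents support neither: nothing indicates which arm would use more excluded therapy, the primary ANCOVA ignores rescue altogether, and the PP analyses already exclude these subjects. Nor do they show that any such subject exists; the claim is that one could.

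**What to change.** - **Trigger.** In SAP 7.4, define the start of the mITT Sub-Analysis and NRI as the first on-treatment use of permitted rescue, or of Appendix B excluded therapy taken for atopic dermatitis or pruritus. Identify it from the eDiary and the concomitant-medication CRF by indication. Keep the Protocol 8.14.2 exception for short use in other indications, and leave the 7.5.4 day counts unchanged.
- **NRI wording.** Make the text of 7.4 and the shell footnotes agree on whether early discontinuation needs a TEAE.
- **Start dates.** SAP 6.5.7 sets a wholly missing medication start to the consent date and a partly missing one to 1 January or the first of the month. That can move on-treatment use to before first dose. For the trigger only, set a missing or partial start that could fall on treatment to the first-dose date or the earliest compatible on-treatment date.
- **WOCF.** Keep it as planned, and add a wider-trigger version in Addendum section 2 as a labelled sensitivity analysis.
- **Timing.** If treatment codes are already open, run all wider-trigger versions as labelled added sensitivity analyses.

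The cost is a few sentences and one medication review. Protocol 8.13 and 8.14.2 already have excluded therapies and drug indication recorded, and Other diary entries are already checked against prohibited products. The downside is that a few more subjects are censored or imputed, including users of milder Appendix B items such as bleach baths or topical antihistamines taken for eczema or itch.

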7.5.5 Patient Reported Local Tolerability

Patient Reported Local Tolerability assesses the following local tolerability symptoms: skin redness and/or color change, itching, burning and/or stinging, pain and/or tenderness, and new or changing rash. Responses are provided according to the following scale:

0 = None 1 = Mild 2 = Moderate 3 = Severe

Each of the 5 questions for local skin tolerability will be summarized by day and treatment as categorical variable (grade) by day and as continuous variable using the score. Patient reported local tolerability will be reported from Day 1 to 7 and in shift tables. Day 1 is the first day of treatment in relation to the previous untreated day and the change in tolerability for subsequent days (Day 2 to Day 7) is in relation to the previous treated day.

7.5.6 Laboratory Data

Clinical laboratory values will be expressed in SI units reported by the central laboratory.

Protocol: PRB244-01 Confidential

STATISTICAL ANALYSIS PLAN

Version 3.0 12-Jan-22

The actual value and change from screening will be summarized for each clinical chemistry, hematology, lipid panel, HbA1C and urinalysis parameters and by each visit. In the event of repeat values, the last non-missing value per visit will be used.

For clinical laboratory values with references ranges classifying the values as low/high/normal/abnormal, shift tables from Baseline to each post-baseline visit will be provided, where values of high and low will be classified as abnormal.

Sample for Serology was collected only at Baseline. Hence, Serology data will be only provided in a listing.

All laboratory data will be also provided in data listings. Values outside of the lab parameter's normal range will be flagged as high, low, or abnormal based on the range of the test.

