10.6.7 Unscheduled/Unanticipated Study visit

If an event arises that requires patient to come in to the research center, subjects should be scheduled for the Unscheduled visit and assessments are performed based on investigator discretion.

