11.1.3 Laboratory Assessments

Blood samples should be taken using standard venipuncture techniques. Blood sampling will be performed according to the site SOPs.

The following laboratory variables will be determined as outlined below:

The following routine clinical chemistry, hematology and Lipid Panel will be performed according to Time and Events table (Appendix A): Albumin, Alkaline Phosphatase, ALT, AST, Total Bilirubin, BUN, BUN: Creatinine ratio, Calcium, Chloride, Creatinine, eGFR, Glucose, Potassium, Sodium, Uric Acid, Total Protein, Bicarbonate

Lipid Panel: HDL Cholesterol, LDL cholesterol, Total Cholesterol, Triglycerides, VLDL Cholesterol, LDL/HDL Cholesterol Ratio, Non-HDL Cholesterol.

Urinalysis: Color, clarity, pH, specific gravity, bilirubin, glucose, ketones, leukocytes, nitrite, blood, protein, urobilinogen, microscopic analysis.

Hematology: WBC, RBC, Hemoglobin, Hematocrit, Platelets, WBC Differential (Neutrophils, Lymphocytes, Monocytes, Eosinophils, Basophils)

Serology will only be done at Screening: HIV Ab, HCV Ab, and HBsAg.

Pregnancy testing: All females of childbearing potential will have a local urine pregnancy test performed at specified visits.

Patients will be asked to fast for at least 8 hours before all blood tests are done. An exception will be made on the laboratory testing for the screening visit such that either fasting or non-fasting blood samples can be collected. This is to avoid requesting participants to fast prior to the informed consent.

The total blood volume collected for clinical labs for Screening visit will be approximately 20 ml of whole blood. Volume collected for subsequent visits would be approximately 10 ml of whole blood.

Any value outside the normal range will be flagged for the attention of the Investigator or designee at the site. The Investigator or designee will indicate whether or not the value is of clinical significance. If the result of the clinical chemistry test from the samples taken during the screening phase is indicated as clinically significant, the study subject will NOT be allowed into the study.

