APPENDIX A: SCHEDULE OF EVENTS

Visit Name	Screening	Washout phase	Baseline Day 0	Day 5	Day 14 (Week 2)	Day 28 (Week 4)	Day 56 (Week 8)	Early Termination Visit	Comments/Clarification
Visit Number	V1		V2		V3	V4	V5		
Visit Window in days	-21 to -14	-14 to -1	0	+/-2	+/-2	+/-2	+/-3		
Informed Consent	X								Informed consent will occur prior to any protocolmandated procedures, including the stopping of any excluded therapies.
Inclusion / Exclusion Criteria	X		X						
Demographics	X								
Medical History	X		X						
Concomitant Medications	X		X		X	X	X	X	
Physical Exam	X						X	X	
Vital Signs	X		X		X	X	X	X	Height and weight will be assessed at screening; BP, pulse, respiration rate, and

									temperature will be assessed at each visit. Smoking status will be recorded at Screening
eDiary	X	X	X	X	X	X	X	X	Subjects will be provided eDiary to be completed at home daily and in-clinic. At home eDiary will include WI-NRS, AI-NRS, rescue medication, dose administration, and local skin tolerability. In clinic eDiary will include POEM and 5-D Pruritus Scale. eDiary will be reviewed at the baseline visit to determine eligibility.
POEM	X		X		X	X	X	X	Patient reported assessment by ePRO
5-D Pruritus Scale	X		X		X	X	X	X	Patient reported assessment by ePRO
IGA	X		X		X	X	X	X	Clinician assessment by eCOA
EASI	X		X		X	X	X	X	Clinician assessment by eCOA
Itch Numeric Rating Scale (NRS)	X	X	X	X	X	X	X	X	Patient reported assessment by ePRO
Clinical Labs	X					X		X	Patients should fast for at least 8 hours before the test but optional at screening. Blood and urine for clinical

								(if visit occurs before Day 28)	chemistry will be shipped to the central lab for processing. Chemistry, Hematology, Lipid Panel, and Urinalysis will be done at Screening and Day 28. Serology will only be done at Screening. Kits and lab manuals will be provided by a central lab.
Urine pregnancy test for WOCBP	X		X			X	X	X	
IWRS			X						
Investigational Product compliance			Х		X	X		X	Weights of dispensed and collected bottles to be recorded following instructions provided to sites.
Dispense study drug			X		X				
Application of study drug			X	X	X	X			First application of study drug will occur in the office under the supervision of the study staff.
Phone call to subjects		X		X					Call to initiate washout phase will be placed once results of screening clinical

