6.5.10 Visit Windows

It is expected that all visits should occur according to the protocol schedule. All visit data will be tabulated per the evaluation visit as recorded on the CRF even if the assessment is outside of the visit window. All ePRO/diary data will be tabulated per the weekly conventions defined in Section 6.5.3. In data listings, the relative day of all dates will be presented.

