Table 14.3.4.1.2 Shift from Baseline for Hematology Parameters (Safety Population)

Early Termination

Repeat for all

Hematology parameters Repeat for Vehicle

[1] Percentage and all subsequent percentages based on the number treated.

[2] Parameters with reference range indicators equal to High or Low are counted as Abnormal.

Source: Listing XXXX

PROGRAM NAME: XXXXXXXXXX

DATE: HH:MM/DDMMMYYYY

- Repeat for 14.3.4.2.2 Shift from Baseline for Chemistry Parameters for Safety Population
- Repeat for 14.3.4.3.2 Shift from Baseline for Urinalysis Parameters for Safety Population

| | | B244 O.D. 5.0 | B244 O.D. 20.0 | Pooled B244 | Vehicle |
|---|----------------|---------------|----------------|--------------|--------------|
| | Statistic | (N=xx) | (N=xx) | (N=xx) | (N=xx) |
| Total Weight Dispensed (g) | n | XX | XX | XX | XX |
| | Mean (SD) | xx.x (xx.xx) | xx.x (xx.xx) | xx.x (xx.xx) | xx.x (xx.xx) |
| | Median | XX.X | XX.X | XX.X | XX.X |
| | Min, Max | XX, XX | XX, XX | XX, XX | XX, XX |
| Total Weight Returned (g) | n | XX | XX | XX | XX |
| | Mean (SD) | xx.x (xx.xx) | xx.x (xx.xx) | xx.x (xx.xx) | xx.x (xx.xx) |
| | Median | XX.X | XX.X | XX.X | XX.X |
| | Min, Max | XX, XX | XX, XX | XX, XX | XX, XX |
| Net Weight of Study Drug (g) [1] | n | XX | XX | XX | XX |
| | Mean (SD) | xx.x (xx.xx) | xx.x (xx.xx) | xx.x (xx.xx) | xx.x (xx.xx) |
| | Median | XX.X | XX.X | XX.X | XX.X |
| | Min, Max | XX, XX | XX, XX | XX, XX | XX, XX |
| Compliance (%) based on IP Weight [2] | n | XX | XX | XX | XX |
| | Mean (SD) | xx.x (xx.xx) | xx.x (xx.xx) | xx.x (xx.xx) | xx.x (xx.xx) |
| | Median | XX.X | XX.X | XX.X | XX.X |
| | Min, Max | XX, XX | XX, XX | XX, XX | XX, XX |
| 50% IP Applied [3] | | | | | |
| Yes | n (%) | xx (xx.x) | xx (xx.x) | xx (xx.x) | xx (xx.x) |
| No | n (%) | xx (xx.x) | xx (xx.x) | xx (xx.x) | xx (xx.x) |
| Number of Dosing Diaries Entered [4] | n | XX | XX | XX | XX |
| | Mean (SD) | xx.x (xx.xx) | xx.x (xx.xx) | xx.x (xx.xx) | xx.x (xx.xx) |
| | Median | XX.X | XX.X | XX.X | XX.X |
| | Min, Max | XX, XX | XX, XX | XX, XX | XX, XX |
| | | | | | |
| Compliance (%) based on Diary Entries [5] | n Mara (CD) | XX | XX | XX | XX |
| | Mean (SD) | XX.X (XX.XX) | XX.X (XX.XX) | XX.X (XX.XX) | XX.X (XX.XX) |
| | Median | XX.X | XX.X | XX.X | XX.X |
| | Min, Max | XX, XX | XX, XX | XX, XX | XX, XX |

Table 14.3.5 Summary of Drug Accountability and Compliance at End of Week 4 (Safety Population)

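### A normal laboratory recheck recorded under Week 4 or Early Termination replaces the abnormal first result in the by-arm summary tables

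*SAP*

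**What the plan says.** SAP 7.5.6 plans two kinds of laboratory table. The first is described as follows: "The actual value and change from screening will be summarized for each clinical chemistry, hematology, lipid panel, HbA1C and urinalysis parameters and by each visit". The repeat rule comes directly after it: "In the event of repeat values, the last non-missing value per visit will be used". The next paragraph turns to parameters with reference ranges: "shift tables from Baseline to each post-baseline visit will be provided, where values of high and low will be classified as abnormal". That paragraph gives no rule for choosing among several values at one visit. Footnote 2 of the hematology shift shell (Table 14.3.4.1.2) adds: "Parameters with reference range indicators equal to High or Low are counted as Abnormal".

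On timing, Protocol Appendix A says: "Chemistry, Hematology, Lipid Panel, and Urinalysis will be done at Screening and Day 28". It also calls for laboratory tests at Early Termination if that visit falls before Day 28. The SAP table shells show Screening, Week 4 and Early Termination.

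On assigning results to visits, SAP 6.5.10 says: "All visit data will be tabulated per the evaluation visit as recorded on the CRF". Protocol 10.6.7 provides for extra attendances, where "subjects should be scheduled for the Unscheduled visit and assessments are performed based on investigator discretion".

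On abnormal results, Protocol 11.1.3 says: "Any value outside the normal range will be flagged for the attention of the Investigator or designee at the site". SAP 7.5.6 also lists all laboratory data, with out-of-range values flagged.

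**The concern.** Change in laboratory parameters is a stated safety endpoint (Protocol 4.2, SAP 3.2.4). At Screening, taking the last value is sensible, because it is the last value before the first dose. After dosing it works differently. An out-of-range result is brought to the investigator's attention, which is a natural reason to repeat the test; a normal result gives no such reason. Protocol 13.7 also asks for adverse events, laboratory values included, to be followed until they normalise or stabilise. If repeats arise in this way, the last value at a visit will tend to be the normal one, partly through regression to the mean.

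The timing of the sample also matters. Protocol 8.6 has all bottles returned at the Week 4 visit, and Appendix A sends samples to a central laboratory. A recheck prompted by the Week 4 result may therefore be drawn off drug. If it is recorded under Week 4, a post-treatment value would stand in the tables for the end-of-treatment value. What is at stake is the by-arm rate of new laboratory abnormalities.

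**Working it through.** The documents give no figure for this rule, so there is nothing of the plan's own to reproduce. The check has two parts.

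**1. Tracing one subject.** Suppose Screening is Normal, the first Week 4 result is Abnormal, and a repeat is Normal.

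| How the repeat is recorded | Week 4 status, last value | Week 4 status, first or worst value |
|---|---|---|
| Under Week 4 | Normal (shift Normal to Normal) | Abnormal (shift Normal to Abnormal) |
| As Unscheduled | Abnormal | Abnormal |

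The table list in SAP Appendix A, section 1.1.3, has no worst post-baseline, maximum-change or any-abnormality table. In the first row, no planned summary recovers the abnormal result. In the second row, nothing is lost.

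**2. Size, under stated assumptions.** None of these inputs is in the documents:
- a normally distributed analyte with a 95% reference range, so 5.0% are out of range without drug;
- correlation (reliability) r between first value and recheck of 0.5, 0.7 or 0.8;
- a share s of abnormal values repeated, 25% to 50%, all recorded under the same visit;
- for the drug example, a shift of +1 SD.

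Let b be the probability that a recheck is in range, given that the first value was out of range. Then

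printed rate = true rate × (1 − s × b).

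Without drug effect, b = 0.815, 0.669 and 0.561 for r = 0.5, 0.7 and 0.8. The two ends of the range are:
- s = 0.25, r = 0.8: 5.0% × (1 − 0.25 × 0.561) = 4.3%, a loss of 14%;
- s = 0.50, r = 0.5: 5.0% × (1 − 0.50 × 0.815) = 3.0%, a loss of 41%.

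With 160 subjects per arm (the evaluable number in SAP 7.1), 5.0% is 8 subjects. The tables would show 8 × 0.86 = 6.9 down to 8 × 0.59 = 4.7.

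With the +1 SD shift, the true abnormal rate on drug is 17.0%, and b is 0.60, 0.47 and 0.38. With half repeated in both arms:

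| r | Vehicle, printed | Drug, printed | Risk difference, points (true 12.0) | Risk ratio (true 3.4) |
|---|---|---|---|---|
| 0.5 | 3.0% | 11.9% | 9.0 | 4.0 |
| 0.7 | 3.3% | 13.1% | 9.7 | 3.9 |
| 0.8 | 3.6% | 13.8% | 10.2 | 3.8 |

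Differences and ratios are taken before rounding. The risk difference loses 15% to 25% of its size. The risk ratio rises, because chance abnormalities return to range more often (56% to 81%) than drug-shifted ones (38% to 60%).

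**The case against.** The strongest objection is that the effect may not arise at all. The rule works within a visit, and results are tabulated under the visit recorded on the CRF. With a central laboratory, a recheck prompted by a result would usually need a later attendance, for which the protocol has an Unscheduled visit. If rechecks are recorded there, the loss is zero. This stands as a condition on the point. It does not dispose of it, because neither document says how rechecks are labelled. The laboratory listing shells offer Screening, Week 4 and Week 8 with no Unscheduled category. They also omit Early Termination, though, so they cannot be read as a complete list of visits.

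Second, the repeat rule sits in the paragraph on values and change, so its use in the shift tables is an inference. That is correct. The inference is reasonable because the shift tables need one status per subject per visit and no other rule is given.

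Third, safeguards exist. Every value is listed with a normality column and an alert flag, investigators judge clinical significance, and an abnormality may be reported as an adverse event. This stands: no data are lost, and no hypothesis test or efficacy result depends on these tables. But listings do not give a rate by arm, which is what the tables are for.

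Fourth, the documents give no repeat rate, reliability or reason for repeats. That most repeats follow an abnormal result is plausible given the flagging rule, but it is an assumption.

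**Conclusion.** The point holds in conditional form. A normal recheck recorded under Week 4 or Early Termination replaces the abnormal first result in the value and change tables and, by inference, in the shift tables. If rechecks are recorded as Unscheduled, nothing is lost. The range of 4.3% to 3.0% for a 5.0% rate rests on the assumed reliability, reference range and repeat share, and on every repeat being recorded under the same visit.

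A reader might infer two stronger things that the documents do not support. One is that any rechecked Week 4 abnormality disappears; this depends on visit labelling, which is not specified, and the value stays in the listings in any case. The other is that a B244 laboratory signal is shrunk towards vehicle in every sense; under the model above this is true of the risk difference only.

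Severity is minor: this is a cheap improvement to the safety summaries, with no bearing on the primary analysis. Confidence is moderate.

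**What to change.** Amend SAP 7.5.6 as follows:
- For Screening, keep the last non-missing value before the first dose.
- For Week 4 and Early Termination, use the first valid scheduled sample in the value and change tables.
- Base the shift tables on the most abnormal valid post-baseline value, including repeat and unscheduled samples. Alternatively, keep the planned shift tables and add one worst post-baseline shift table of this kind.
- Exclude samples that the laboratory reports as invalid.
- List all repeats, and state how rechecks are assigned to visits.

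The cost is a short change to one SAP section and a selection flag in the laboratory analysis dataset. There are two small downsides. Printed abnormal rates will rise slightly. A subject's change value and shift status may also come from different samples, which a table footnote should state.
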